## ***Hypothesis:***

1. It is hypothesized that subjects having a PS TKA will experience greater posterior femoral rollback, axial rotation and weight-bearing flexion than subjects having a PCR TKA.
2. It is hypothesized that subjects having a Persona TKA will experience better kinematic patterns than subjects previously analyzed having a NexGen TKA.

***Study design:*** In vivo knee kinematics will be assessed for 25 subjects that have been implanted with a Zimmer-Biomet Persona fixed bearing posterior stabilizing (PS) total knee arthroplasty (TKA) by [name] [name] of the Institute for Locomotion, Aix-Marseille University, Hopital Sainte-Marguerite. The other 25 subjects with the Zimmer-Biomet Persona fixed bearing poster cruciate retaining (PCR) TKA will be provided by another surgeon at a separate site, which has yet to be determined. [name] and [name] both of the Institute for Locomotion, Aix-Marseille University, Hopital Sainte-Marguerite will serve as Sub-Investigators. [name] of the University of Tennessee will also serve as a Sub-Investigator. Enrollment will be increased to 28 subjects per implant type to ensure that researchers acquire the necessary 25 usable datasets for analysis for each implant type and also

to account for any subjects that may drop out of the study. All TKAs should be judged clinically successful (KSS > 75). Each subject should have a well-functioning prosthesis, be at least six months post-operative, and should have good-to-excellent post-operative passive flexion.

Deciding which subjects received which kind of implant was up to the discretion of the study surgeon, according to his professional opinion. The determination as to which type of implant subjects received is outside the scope of this particular study. Subjects will already have the knee implants and must be at least six months post-operative.

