#### ***Inclusion and exclusion criteria:***

We will use the following inclusion criteria to recruit participants for this study:

1. Subjects will have a Zimmer Persona fixed bearing PS TKA.
2. Subjects must be at least six months post-operative.
3. Subjects will have KSS greater than 75.
4. Participants must be able to perform the required activities - stepping up and a deep knee bend.
5. Subjects must be willing to sign the Informed Consent (IC) / HIPAA form to participate in the study.
6. Bilateral subjects may be included in the subject population.

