#### **Exclusion criteria:**

1. Pregnant, potentially pregnant or lactating females. To satisfy radiation protocol, each female subject will be asked if she is pregnant, or possibly could be pregnant. A pregnant person will not be allowed to participate in the study. To ensure this, a pregnancy test will be administered to any female participants of child bearing age who have not had a hysterectomy.
2. Subjects without the required type of knee implant.
3. Subjects who are unable to perform stepping up and deep knee bend.
4. Subjects who are unwilling to sign Informed Consent/HIPAA documents.
5. Subjects who do not speak English and/or French.

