### **Private Health Information/Medical Record Data**

The surgeon and his staff will provide subjects' clinical information from their medical records – PHI – to [name] and his researchers to aid in the interpretation of the results and correlate clinical outcomes versus kinematic results, although only researchers present during data collection or those appointed by [name] to lead the study will have access to PHI; they will sign confidentiality statements. This information can be used to rule out any unique

kinematic patterns. This information will only be used by the UT researchers and will not be provided to any other source.

The clinical/demographic information acquired from the medical records with participant authorization obtained as required by HIPAA will include:

- the range-of-motion (at least 6 months post-operative),
- DOB, body weight, Body Mass Index (BMI),
- date of surgery,
- Subjects post-operative KSS (must be >75),
- previous medical assessments that are not a part of this particular research study, that may alter the kinematic results, such as previous knee x-rays,
- post-operative time and any other conditions that may alter the kinematic results, such as back problems, ankle fusion, or contra-lateral knee problems.

The surgeon's office will also relate the implant component information and surgical technique details:

- Size of: femur, tibial plate, articular surface thickness [mm], patella
- Product/Reference # of: femur, tibial plate, polyethylene (PE) insert, patella
- Lot # of: femur, tibial plate, PE insert, patella
- Surgical operation notes
- Use (if any) and details of intraoperative surgical technologies, such as robotic assistance, subject-specific cutting guides, surgical navigation, etc.

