## DATA ANALYSIS

Once the subjects have completed the activity, the fluoroscopic videos will be stored digitally and specific frames of interest will be captured from the video and exported into the preprocessing software. The specific frames of interest will be full extension, maximum knee flexion (both inclusive), and 30° knee flexion increments during the complete flexion cycle.

Our 3D to 2D registration technique will be used to overlay the 3D models of the implanted components on their projection in the 2D fluoroscopic image. The fluoroscopic video would be digitized into frames and corrected for distortion. From here, the distortion-free images would be used with the 3D to 2D registration technique to extract in vivo patient femorotibial kinematics, which involves overlaying the 3D models of the components on their projection in the 2D fluoroscopic image.

Statistical analysis of the data will be carried out to analyze the two cohorts. All variables, except for lift-off and VAG, will be denoted as continuous. The data will be first checked for normality using the Shapiro-Wilk test. Only when the data is found to be normally distributed will parametric tests be used; otherwise, non-parametric tests will be used. The data will also be tested for equality of variance using the Barlett's test and Levene's test. The final selection criterion for the type of test to conduct will be based on the check for normality, as well as the check for equal variance. Therefore, for all the continuous variables, the following tests will be used:

1. Student's t-test (when the data is normally distributed and has equal variance).
2. Welch Anova test (when the data is normally distributed but has unequal variance).
3. Wilcoxon Mann Whitney U-test (when the data is not normally distributed).

Lift-off, as applicable, will be treated as a categorical variable in this study and a contingency analysis using the Fisher's exact test will be carried out. All statistical tests will be carried out at 95% confidence level ( $\alpha=0.05$ ) and will be performed using JMP® Statistical Discovery™ (SAS Institute Inc., Cary, NC) software.

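### Back, ankle and opposite-knee conditions that the protocol says may alter the kinematics are collected but enter no PS-PCR test, so an imbalance between the cohorts could bias the comparison

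*Protocol*

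**What the plan says.** **Collection and stated use.** The protocol section Private Health Information/Medical Record Data lists, among the items taken from the records, "any other conditions that may alter the kinematic results, such as back problems, ankle fusion, or contra-lateral knee problems". The record data serve "to aid in the interpretation of the results and correlate clinical outcomes versus kinematic results". A further, optional use follows: "This information can be used to rule out any unique" kinematic patterns. No rule or model accompanies any of these uses.

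**Eligibility.** No criterion names the back, the ankle or the opposite knee. The function-related exclusion is "Subjects who are unable to perform stepping up and deep knee bend". The inclusion list adds "Subjects will have KSS greater than 75" and also states "Bilateral subjects may be included in the subject population". The Study design paragraph further asks for a prosthesis that works well and for good passive flexion. Under Recruitment, the PS surgeon puts forward patients whose condition lets them do the activities.

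**Formation of the cohorts.** "Deciding which subjects received which kind of implant was up to the discretion of the study surgeon". The PS subjects come from one surgeon at one institute. The PCR subjects come from another surgeon at a site not yet chosen. The target is 25 usable datasets per implant type, from 28 enrolled.

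**Analysis.** The SAP states: "Statistical analysis of the data will be carried out to analyze the two cohorts". For continuous variables it offers Student's t-test, the Welch test or the Mann-Whitney test, and for lift-off Fisher's exact test. It names no covariate, stratification, matching, balance table or sensitivity analysis.

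**The concern.** Hypothesis 1 predicts more rollback, axial rotation and weight-bearing flexion with PS than with PCR. The deep knee bend is a standing movement taken to the subject's own maximum, and the Data Collection section tells subjects to stop at the first sign of pain. A painful back, a fused ankle or a bad opposite knee could therefore end the bend early, whatever the implant.

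If one cohort has more such subjects, an unadjusted test attributes their deficit to the implant. With equal shares there is no bias, only extra variance that could have been reduced. The protocol itself names the conditions as relevant and already collects them, so leaving them out of the comparison is an avoidable gap.

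**Working it through.** The documents state no effect size, SD, power or prevalence, so there is no planned figure to reproduce. The check has two parts.

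**1. Reading the passages together**

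| Question | Answer in the documents |
|---|---|
| Are the conditions expected to affect the outcome? | Yes (protocol, Medical Record Data) |
| Are they collected? | Yes (same section) |
| Are affected subjects excluded? | Not by name; screened only indirectly |
| Is balance between the cohorts secured? | No; surgeon's choice of implant, different surgeons and sites |
| Do they enter a PS-PCR test? | No (SAP, Data Analysis) |

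**2. Illustration of size**

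From the documents: 25 per cohort and alpha 0.05. Sidedness is not stated; two-sided is assumed.

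Assumed, not in the documents: an affected subject loses 8-12 degrees of weight-bearing flexion; the SD among subjects of the same status is 12-15 degrees; there is no true implant effect; three pairs of prevalences.

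Spurious difference = (difference in prevalence) x (degrees lost). Dividing by the SD gives the shift in SD units.

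- 40% v 15%: 0.25 x 8 = 2.0 degrees to 0.25 x 12 = 3.0 degrees; 2.0/15 = 0.13 SD to 3.0/12 = 0.25 SD.
- 25% v 15%: 0.10 x 8 = 0.8 degrees to 0.10 x 12 = 1.2 degrees; 0.8/15 = 0.05 SD to 1.2/12 = 0.10 SD.
- Equal shares: 0.

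Student's t-test was simulated with each subject affected or not at the stated prevalence (200,000 runs per cell):

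| Affected | 8 degrees, SD 15 | 12 degrees, SD 12 |
|---|---|---|
| 40% v 15% | 7.3% | 12.5% |
| 25% v 15% | 5.3% | 6.2% |
| 25% v 25% | 4.9% | 4.9% |

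Treating the 40% v 15% case as a pure shift, without the extra variance from mixing affected and unaffected subjects, gives 7.5% at 0.13 SD and 13.9% at 0.25 SD (noncentral t, 48 degrees of freedom).

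With implant and the flag both in a linear model, rejection at 40% v 15% returns to 5.2% (8 degrees, SD 15) and 4.8% (12 degrees, SD 12), from 20,000 runs each.

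A significance test of balance would not settle the matter. With 25 per group, a true 10% v 30% imbalance would be significant only about 42% of the time.

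**The case against.** **The data are not ignored.** This is correct. The protocol gives them interpretive and correlational uses as well as the optional ruling out of unusual patterns, so a reader who infers that they go unused is mistaken. None of these uses is a rule for comparing PS with PCR. If ruling out means removing subjects after their patterns have been seen, that would be an exclusion dependent on the outcome.

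**The screens already remove the worst cases.** This stands in part. KSS above 75, a sound prosthesis, good passive flexion and ability to do both activities probably lower both the prevalence and the effect of these conditions. They mostly describe the index knee, however, and do not make two separately recruited cohorts alike. The surgeon's recommendation step is described only for PS patients.

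**The size is assumed.** This stands in full. A 40% v 15% imbalance has no basis in the documents, and at 25% v 15% the inflation is slight. A reader might infer that comorbidity alone could decide Hypothesis 1. A spurious 2-3 degrees and a rejection rate of 7-13% do not support that, and nothing has been quantified for rollback or axial rotation.

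**Adjustment leaves the larger problem.** This also stands. Surgeon and site coincide completely with implant type, and no comorbidity covariate can separate them. Each surgeon's office supplies its own records, so the conditions may also be recorded differently in the two cohorts.

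**Conclusion.** The gap is real and moderate. The plan names and collects conditions that it expects to alter the outcome, admits subjects who have them, and then compares two non-randomised cohorts without using them. An imbalance can bias the PS-PCR comparison in either direction.

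The documents cannot show how large the bias is or which way it runs. The illustrated false-positive rates, from about 5% to about 13%, rest wholly on the assumed prevalences, degrees lost and SD, and apply to flexion only. The point justifies an inexpensive addition to the SAP. It does not show that the study's conclusion would be wrong, and it does not call for a change in eligibility.

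**What to change.** 1. Before image registration, code one yes/no flag per knee for a condition outside the index knee that may alter kinematics, and record its type. Use one written definition at both sites. It must say whether a well-functioning replacement of the opposite knee counts, because bilateral subjects are allowed.
2. Tabulate the flag by cohort and judge balance from the counts, without a significance test.
3. Keep the SAP tests. For each continuous outcome add a pre-specified linear model with implant and the flag. Use robust standard errors where the SAP would select Welch, and fit the model on ranks where it would select Mann-Whitney.
4. Add a sensitivity analysis restricted to unflagged knees, using the SAP tests, including Fisher's exact test for lift-off.
5. State that no subject is dropped after the kinematic pattern has been seen.
6. State that none of this removes confounding by surgeon and site.

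**Cost.** SAP wording, an agreed definition and one coded column from data already abstracted. The flag takes one of 48 residual degrees of freedom. The restricted analysis loses knees: at the assumed 40% and 15%, about 25 x 0.60 = 15 and 25 x 0.85 = 21 would remain. A composite flag treats different conditions as having one effect, a compromise that 25 per cohort makes reasonable.

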## SPECIFIC RISKS AND PROTECTION MEASURES

### 1. Fluoroscopic Procedures

As with every clinical study, there may be some risks. However, doses of radiation exposure received will be much lower than those known to produce detectable health effects. Previously reported literature shows that fluoroscopy-based procedure (angiography) on the lower limb result in a typical effective dose of 0.83 mSv per min (0.083 rem per min) (Verdun). Mettler, et al. have reported that the typical effective dose for a conventional knee procedure is 0.005 mSv (0.0005 rem). According to either estimate, the additional risk of a fluoroscopic procedure involving the knee ranges between "Negligible" to "Low" for a 2 minute exam (Verdun). A previous fluoroscopy TKA study conducted at another hospital with a 2 minute on-time limit shows that the average effective dose was 0.14 mSv (0.0014 rem) with a maximum dose of 0.27 mSv (0.027 rem). The additional risk for all subjects in this previous study would be considered "Negligible." To account for subject variability and differences in imagining techniques, all subjects enrolled in this study will receive fewer than 2 rem. 2 rem is considered "Low" risk. It is unlikely that anyone in this study will approach the 2 rem limit. Since the fluoroscopy data will be collected in one session, there will only be one day in which the participants will be exposed to this amount of radiation.

In conclusion, a participant who will be fluoroscoped for less than two minutes will be exposed to a *maximum* amount of only 2.0 rems of radiation. This means that the maximum total exposure rate will be less than 2 rems per subject for the entire experiment (Attachments 3 and 4). The participant's knee joint will be fluoroscoped using negligible to low risk levels of radiation according to published literature (Attachments 2 and 3).

The participant has the right to stop the procedure at any time; researchers or the RT can end the procedures at any time if they feel the participant is at risk, but the participant can choose to remain in the study if s/he feels that there is no risk to her/his surgical procedure or recuperation.

---

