**Table 4****What to Tell Your Patients concerning Additional Risk of Death from Cancer**

| Effective Dose (mSv) | Risk       | Quantification           | Examination  |
|----------------------|------------|--------------------------|--|
| <0.1                 | $<10^{-6}$ | Negligible               | Radiography of the chest (postero-anterior), extremities, or teeth |
| 0.1–1.0              | $10^{-5}$  | Minimal or extremely low | Abdomen, lumbar spine  |
| 1.0–10               | $10^{-4}$  | Very low                 | CT of the brain, chest, or abdomen                                 |
| 10–100               | $10^{-3}$  | Low                      | Multiphase CT  |
| >100                 | $>10^{-2}$ | Moderate                 | Interventional procedures,* repeat CT                              |

Sources.—References 10 and 22.

\*Including the deterministic effects of ionizing radiation (skin burns).

## ATTACHMENT 2

Mettler, et al. "Effective Doses in Radiology and Diagnostic Nuclear Medicine." *Radiology* 248.1 (2008): 254-263. <http://radiology.rsna.org/content/248/1/254.full.pdf+html>

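### Does the tenfold slip in the prior study's rem figure, and its Negligible label, change the protocol's radiation-risk case?

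*Protocol*

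**What the plan says.** The radiation case is in the Protocol, Specific Risks and Protection Measures, item 1 (Fluoroscopic Procedures). It rests on three sources of dose and one ceiling.

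- A literature rate for lower-limb angiography: "a typical effective dose of 0.83 mSv per min (0.083 rem per min". Attachment 1, Table 2 gives its basis.
- A literature value for a conventional knee examination, 0.005 mSv, also found in Attachment 2.
- A previous knee-replacement fluoroscopy study with the same two-minute limit, where "the average effective dose was 0.14 mSv (0.0014 rem) with a maximum dose of 0.27 mSv (0.027 rem".
- For the present study, a ceiling of 2 rem per subject, labelled Low.

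On risk classes, the section begins one sentence "According to either estimate, the additional risk of a fluoroscopic procedure involving the knee ranges between" and gives the range as Negligible to Low for a two-minute examination. Of the previous study it says: "The additional risk for all subjects in this previous study would be considered" Negligible. The classes come from Table 4 in Attachment 1, where 0.1 to 1.0 mSv is "Minimal or extremely low". The ceiling is referenced to "Attachments 3 and 4", and the closing negligible-to-low statement to Attachments 2 and 3.

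**The concern.** Fluoroscopy is the study's central research procedure, and this section is the justification for it. The previous study resembles this one in joint and time limit, so a reader would naturally use it to judge expected exposure. Its mean is printed with two values that cannot both be right. Its risk label is also more favourable than the table the protocol reproduces. The references compound this: Attachment 4 is the knee score form, while the table that defines the labels is in Attachment 1.

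If the present study's own dose bound or risk class rested on those figures, an ethics committee would be approving an understated risk, and any text for participants drawn from the section would carry the error forward. That is the question to settle.

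**Working it through.** **Inputs.** Dose pairs and the ceiling: Protocol, Fluoroscopic Procedures. Lower-limb angiography, 5.0 mSv over 6 minutes: Attachment 1, Table 2. Risk classes: Attachment 1, Table 4, namely below 0.1 mSv Negligible (risk below 10^-6); 0.1–1.0 Minimal or extremely low (10^-5); 1.0–10 Very low (10^-4); 10–100 Low (10^-3).

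**Step 1: reproduce the literature rate.** 5.0 / 6 = 0.833 mSv per minute, which agrees with the printed 0.83.

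**Step 2: check each unit pair with rem = mSv / 10.**

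| Dose | mSv | mSv / 10 | Printed rem | Result |
|---|---|---|---|---|
| Angiography, per minute | 0.83 | 0.083 | 0.083 | agrees |
| Conventional knee examination | 0.005 | 0.0005 | 0.0005 | agrees |
| Previous study, mean | 0.14 | 0.014 | 0.0014 | differs tenfold |
| Previous study, maximum | 0.27 | 0.027 | 0.027 | agrees |

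Only the mean fails. As printed, the maximum is 0.27 / 0.14 = 1.9 times the mean in mSv but 0.027 / 0.0014 = 19 times the mean in rem. The documents do not show which of the two figures is mistyped.

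**Step 3: test the label under both readings.**

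- If 0.14 mSv is right, the mean is in the 0.1–1.0 class.
- If 0.0014 rem is right, the mean is 0.014 mSv, which is Negligible.
- The maximum is 0.27 mSv in either unit, 0.27 / 0.1 = 2.7 times the upper limit of Negligible.

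So a Negligible label for all subjects contradicts Table 4 under either reading. For the maximum, the class is one higher, and the nominal risk goes from below 10^-6 to 10^-5, a step of at least ten.

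**Step 4: place every quoted dose in Table 4.**

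| Dose | mSv | Table 4 class |
|---|---|---|
| Knee examination | 0.005 | Negligible |
| Previous study, mean (either reading) | 0.014 or 0.14 | Negligible, or Minimal or extremely low |
| Previous study, maximum | 0.27 | Minimal or extremely low |
| Angiography, two minutes: 2 × 0.83 | 1.66 | Very low |
| This study's ceiling: 2 rem × 10 | 20 | Low |

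All five lie within Negligible to Low, the overall range the protocol gives. The 1.66 mSv value sits inside that range, so the upper end overstates what the literature figures require.

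**Step 5: see whether anything in this study is computed from the faulty figures.** The ceiling is 20 / 0.27 = 74 times the previous maximum and 20 / 1.66 = 12 times the two-minute literature figure. The section presents it as an allowance for variation between subjects and in imaging, not as a value derived from the previous study's mean. The two-minute limit is set separately, and on-time is recorded for each subject (Protocol, Data Collection). The SAP's Data Analysis section uses no dose variable.

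**The case for a change.** The best argument for acting is that this is a safety statement, where accuracy matters for its own sake. The label error does not depend on the unit error, because it persists whichever figure for the mean is correct. The previous study is the closest comparator offered. A committee member who follows the citation for the ceiling lands on a position statement and a questionnaire, not on the table that shows the label to be wrong. Putting it right costs only a few words.

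Part of that stands: the unit pair is inconsistent, the label contradicts Table 4, and the reference to Attachment 4 points to the wrong document.

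Three further claims do not stand. It cannot be said that the mean dose is understated, because the documents do not show which unit is in error. The two-minute literature figure is not a discrepancy, because its class falls inside the stated range. The references are not wholly misplaced: Attachment 2 holds the 0.005 mSv knee figure, Attachment 3 is a position statement on radiation risk, and the risk-class sentence itself names the paper reproduced in Attachment 1. Nor can an error in participant-facing text be shown, since the consent pages are not in the material available for review.

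**Conclusion.** These are clerical slips in the description of a past study: one unit pair out by a factor of ten, one label a class too low for the maximum (0.27 against a limit of 0.1 mSv), and one wrong attachment number. The sentences need to be reconciled with each other and with Table 4, and the mean checked against its source, which routine editing would do.

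No change to the plan follows. The statements that govern this study already agree with the protocol's own table: the ceiling of 2 rem is 20 mSv and is Low, and the overall range runs from Negligible to Low. Correcting the previous study's figures moves that study within a range already disclosed and leaves the limits, procedures, endpoints, tests and risk conclusion as they are.

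This rests on two assumptions: that Table 4 is the scale behind the section's risk labels, and that the maximum, which is consistent in both units, is correctly reported.
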